**LIST OF ABBREVIATIONS**

CVT	Cerebral venous thrombosis
DOACs	Direct oral anticoagulants
VKA	Vitamin K antagonists
RCT	Randomized controlled trial
NIHSS	National Institutes of Health Stroke Scale
mRS	Modified Rankin Scale
MRV	Magnetic resonance venography
CTV	Computed tomography venography
DSA	Digital Subtraction Angiography
ICH	Intracranial hemorrhage
ISTH	International Society on Thrombosis and Haemostasis

## SUMMARY

**Rationale:** Cerebral venous thrombosis (CVT) is a rare condition. Once the diagnosis is established, current guidelines consistently recommend the early initiation of anticoagulation therapy with heparin, even in the presence of intracerebral hemorrhage. Upon clinical and radiological stabilization, treatment is typically transitioned to oral anticoagulants, including either vitamin K antagonists (VKA) or direct oral anticoagulants (DOACs). Since 2019, emerging evidence from randomized controlled trials such as RESPECT-CVT, CHOICE-CVT, and SECRET, along with large-scale international observational studies including ACTION-CVT and DOAC-CVT has demonstrated that DOACs can be safely used in the treatment of CVT. However, due to the rarity of the condition, most existing studies are limited by small sample sizes. Therefore, there is a growing need for additional studies across diverse geographic regions to expand the global evidence base on DOACs use in CVT. Such data will help enable more accurate assessment and analysis of treatment outcomes in patients with CVT receiving DOACs therapy.

**Objective:** To evaluate treatment outcomes of DOAC therapy in CVT patients.

**Study Design:** A prospective cohort study at Bach Mai Hospital, Vietnam, enrolling a minimum of 69 patients with CVT treated with DOACs.

**Study Population:** Adult patients ( $\geq 18$  years old) with radiologically confirmed CVT, treated with therapeutic-dose heparin in the acute phase and subsequently with a direct oral anticoagulant. All will be recruited from Bach Mai Hospital, the national referral center for CVT in northern Vietnam.

**Primary study endpoint:** the primary endpoint is a composite of the number of patients who experience either major bleeding, as defined by the International Society on Thrombosis and Haemostasis (ISTH), or a venous thromboembolic event (VTE) - including recurrent CVT, deep vein thrombosis of any limb, pulmonary embolism, or splanchnic vein thrombosis — within up to 6 months of follow-up.

**The secondary endpoint:**

- Mortality Rate: all death from any cause during the 6-month follow-up.
- Functional outcome: proportion of patients with mRS 0–1 at 3 and 6 months.
- Number of participants with major bleeding events
- Number of participants with clinically relevant non-major bleeding (CRNMB) events
- Number of participants with symptomatic recurrent venous thromboembolism (VTE)
- Number of participants who discontinued anticoagulant therapy early
- Number of participants with arterial thrombotic events
- Number of participants with arterial thrombotic events
- Serial D-dimer measurements after CVT
- Venous recanalization
- Frequency of chronic headache after CVT

**Nature and Extent of Risks, Burdens, and Benefits:** This study is non-interventional in nature and does not introduce any additional procedures, risks, or burdens for participants. All information utilized will be obtained exclusively from standard clinical care and follow-up, without altering the course of treatment. No experimental interventions will be administered, and participation does not affect patients' access to care or outcomes.

ClinicalTrials.gov Identifier:

## 1. INTRODUCTION AND RATIONALE

CVT accounts for only 0.5-1% of all diagnosed and treated stroke cases worldwide. Previous studies have demonstrated that patients with CVT typically exhibit distinct clinical characteristics compared to those with other types of stroke. Notably, disproportionately affects younger individuals, with the majority of cases occurring in patients under 50 years of age and approximately two-thirds involving women. Clinically, CVT often presents with symptoms associated with elevated intracranial pressure or focal brain parenchymal lesions, which may or may not be associated with mass effect.

Current international guidelines uniformly recommend initiating treatment with low-molecular-weight heparin (LMWH) or unfractionated heparin during the acute phase. Once the clinical status and imaging findings have stabilized, oral anticoagulation is advised for a duration of 3-12 months, depending on the patient's individual risk profile.

In recent years, increasing attention has been directed toward the safety and efficacy of DOACs in the management of CVT. The first randomized controlled trial (RCT) evaluating DOAC use in CVT was the RESPECT-CVT trial, published in 2019, which assessed dabigatran. This was followed by CHOICE-CVT, was conducted in China. Both studies compared dabigatran with vitamin K antagonists (VKAs) and found no significant differences in safety and efficacy between the two groups. In 2023, the SECRET trial - an RCT comparing rivaroxaban with VKA - reported comparable outcomes. However, due to the rarity of CVT, all of these RCTs were limited by relatively small sample sizes, underscoring the inherent difficulty of conducting large-scale RCTs for rare conditions.

To complement these findings, large multicenter observational studies have been undertaken. Notably, the ACTION-CVT and DOAC-CVT studies have provided real-world evidence supporting the use of DOACs, demonstrating comparable safety and effectiveness to VKAs. DOACs also offer several practical advantages, including fixed dosing, fewer drug-food interactions, and no requirement for routine INR monitoring. Nevertheless, even these observational studies have not enrolled patient numbers in the thousands, thereby limiting the statistical power for robust subgroup analyses.

## **Study protocol: Treatment Outcomes of DOACs in CVT: A Prospective Study in Vietnam**

Recent international guidelines now permit the use of either VKAs or DOACs in the treatment of CVT, acknowledging the growing body of evidence indicating similar safety and efficacy profiles. Research in this area remains ongoing worldwide.

In Vietnam, research on CVT treatment outcomes - particularly regarding the use of DOACs - is still limited. Moreover, due to the rarity of the condition and the complexity of evaluating multiple risk factors, patients with CVT are typically referred to major stroke centers for specialized management. Consequently, patient cohorts from such tertiary centers may provide insights that are representative of the national CVT population, rather than being confined to local or institutional patterns.

The primary objective of the present study, Treatment Outcomes of DOACs in CVT, is to evaluate the real-world safety and efficacy of DOACs in the management of CVT in Vietnam. The secondary objective is to assess clinical outcomes and identify factors associated with treatment response during follow-up.

## **2. OBJECTIVE**

### **Primary Objective**

To evaluate the effectiveness and safety of DOACs in patients with CVT over a 6-month follow-up period, using the composite outcome of major bleeding events or recurrent venous thromboembolism.

### **Secondary Objectives**

Patients with CVT treated with DOACs will be assessed at 3 and 6 months to determine the following clinical outcomes:

- Mortality Rate
- Functional outcome
- Number of participants with major bleeding events
- Number of participants with clinically relevant non-major bleeding (CRNMB) events
- Number of participants with symptomatic recurrent venous thromboembolism (VTE)

[figure not shown]
## **Study protocol: Treatment Outcomes of DOACs in CVT: A Prospective Study in Vietnam**

- Venous recanalization
- Number of participants who discontinued anticoagulant therapy early
- Number of participants with arterial thrombotic events
- Frequency of participants with chronic headache after CVT
- Health-related quality of life (EQ-5D-5L utility index score)
- Serial D-dimer measurements after CVT

### 3. STUDY DESIGN

*Treatment Outcomes of DOACs in CVT* is a prospective, single-center observational study. The study involves the collection of treatment data during both the acute hospitalization phase and subsequent outpatient follow-up. It was conducted at Bach Mai Hospital, a central and tertiary referral center for the management of cerebral venous thrombosis (CVT) in Vietnam.

A schematic diagram of the study design and follow-up is provided below

## 4. ELIGIBILITY CRITERIA

### 4.1. Population

All consecutive adult patients diagnosed with CVT at Bach Mai Hospital were considered eligible for inclusion. Patients could be enrolled during initial hospitalization or through the outpatient stroke clinic. Both newly diagnosed cases and those referred from other facilities for further management were included.

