### 4.2. Inclusion criteria

- Signed informed consent (ICF) to participate in the study
- Age  $\geq$  18 years
- Confirmed diagnosis of cerebral venous thrombosis (CVT) based on clinical presentation and neuroimaging, including one or more of the following:

MRI and MRV, AND/OR

CT and CTV, AND/OR

MRI or CT combined with DSA

- Initiation of DOACs within 5 to 15 days after starting treatment with heparin

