## **5.2. Study procedures**

Baseline clinical and radiological data, including patient demographics, risk factors, imaging findings, anticoagulant treatment details, and in-hospital events during the acute phase of CVT, will be collected for all enrolled patients.

Participants will be followed up at 3 and 6 months after diagnosis. Data collected at these time points will include:

- Type and duration of oral anticoagulant therapy
- Clinical events, including recurrent thrombotic or bleeding events
- Degree of disability will be assessed using mRS
- Venous recanalization will be assessed at 6 months using brain MRI with venography or CT venography. Recanalization will be categorized as complete, partial, or none, based on the classification proposed by Aguiar de Sousa et al
- Health-related quality of life, evaluated using the EQ-5D-5L instrument. This tool evaluates five domains (mobility, self-care, usual activities, pain/discomfort, and anxiety/depression), each with five levels of severity. A utility index score will be calculated using the Vietnamese EQ-5D-5L value set, ranging from -0.511 to 1.000, where 1.000 indicates perfect health, 0.000 corresponds to death, scores below 0 indicate health states considered worse than death by the general Vietnamese population.
- Presence of chronic headache, defined as a headache occurring on  $\geq 15$  days per month and persisting for more than 3 months following the acute CVT event, consistent with the International Classification of Headache Disorders, 3rd edition

(ICHD-3). Headache-related disability, assessed using the Headache Impact Test (HIT-6)

All data will be collected as part of routine clinical care during outpatient visits or structured telephone interviews and recorded using standardized case report forms.

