## **6. STATISTICAL ANALYSES**

All statistical analyses will be conducted using R software (version 4.4.1). Statistical significance will be set at a two-sided p-value < 0.05.

Descriptive statistics will be used to summarize baseline characteristics. Continuous variables will be reported as means  $\pm$  standard deviations (SD) or medians with interquartile ranges (IQR), depending on distribution. Categorical variables will be expressed as counts and percentages.

The primary endpoint: a composite of major bleeding (per ISTH criteria) or symptomatic recurrent venous thromboembolism (VTE), including cerebral venous thrombosis, deep vein thrombosis, pulmonary embolism, or splanchnic vein thrombosis—will be analyzed as a time-to-event outcome. Kaplan–Meier survival curves will be constructed, and group comparisons will be performed using the log-rank test. Cumulative event rates at 6 months will be reported with 95% confidence intervals.

For secondary endpoints, the following analyses will be conducted:

- Functional outcome (mRS 0-1 vs 2-6 at 3 and 6 months) will be analyzed using logistic regression to identify predictors of favorable recovery.

- Venous recanalization status at 6 months will be described as complete, partial, or absent, based on follow-up imaging, and summarized as proportions.
- Rates of major bleeding, any bleeding, symptomatic recurrent VTE, and arterial thrombotic events will be summarized descriptively and reported with 95% confidence intervals.
- Health-related quality of life (EQ-5D-5L), chronic post-CVT headache (HIT-6), at 3 and 6 months will be compared using paired t-tests or Wilcoxon signed-rank tests, as appropriate.
- Changes in D-dimer levels from baseline to follow-up will be analyzed using paired tests and visualized longitudinally.

Missing data will be handled using complete case analysis. If the missing rate exceeds 10% for any variable, sensitivity analyses will be performed.

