## **7. ETHICAL CONSIDERATIONS**

This study is a doctoral research project conducted as part of the PhD training program at Hanoi Medical University. The study was officially approved by the university on March 3, 2025, under Decision No. 580/QĐ-DHYHN.

Ethical approval was granted by the Ethics Committee of Bach Mai Hospital on July 4, 2025, under Decision No. 45/BM-HĐĐĐ. The study will be conducted in accordance with the principles of the Declaration of Helsinki (2013) and Good Clinical Practice (GCP) guidelines. The research will take place at Bach Mai Hospital, a national tertiary referral center for cerebrovascular diseases in Vietnam.

All eligible participants will be required to provide written informed consent before enrollment. Patients will be informed of the study's purpose, procedures, potential risks and benefits, their rights to confidentiality, and the option to withdraw from the study at any point without affecting their ongoing care.

This is a prospective, observational study. All interventions and follow-up procedures are part of standard clinical management for patients with cerebral venous thrombosis (CVT).

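### With open-ended clinic and referral enrolment, follow-up counted from diagnosis and no delayed entry, 6-month mortality and fatal primary events are biased low

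*Protocol*

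**What the plan says.** Section 4.1 opens with consecutive recruitment: "All consecutive adult patients diagnosed with CVT at Bach Mai Hospital were considered eligible for inclusion". It then gives two entry routes, "Patients could be enrolled during initial hospitalization or through the outpatient stroke clinic", and widens the source population: "Both newly diagnosed cases and those referred from other facilities for further management were included".

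The only timing rule in Section 4.2 is "Initiation of DOACs within 5 to 15 days after starting treatment with heparin". It links two treatment dates to each other. It does not link either of them, or the diagnosis, to the date of consent. Section 7 adds that "All eligible participants will be required to provide written informed consent before enrollment".

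Section 5.2 sets the clock: "Participants will be followed up at 3 and 6 months after diagnosis". For the primary endpoint, Section 6 says that "Kaplan–Meier survival curves will be constructed, and group comparisons will be performed using the log-rank test", and that the cumulative 6-month rate will be given with a 95% confidence interval. It mentions neither delayed entry nor a landmark. The Summary lists as a secondary endpoint "Mortality Rate: all death from any cause during the 6-month follow-up". Fatal bleeding counts as major bleeding in Appendix B, and death is mRS 6, which Section 6 places in the unfavourable class.

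**The concern.** A patient treated at another hospital who started a DOAC inside the permitted interval and first attends the stroke clinic two months later meets every criterion. An otherwise identical patient who died in those two months cannot consent and so cannot be counted. The first patient nevertheless brings two months into a risk period that starts at diagnosis, months during which death was impossible for anyone entering this way. This is left truncation, often called immortal time.

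The primary objective is the effectiveness and safety of DOACs, and the planned analysis concentrates on the DOAC patients. An understated death rate therefore goes straight into the main safety message, with no comparison group to offset it. Section 8 discusses the single centre, the sample size, the VKA patients and missing data, but not selection by survival to enrolment. The same section says the hospital takes referrals from provincial and district hospitals, so the route is a real one.

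**Working it through.** **Inputs.** From the protocol: two entry routes, no enrolment window, consent required, clock from diagnosis, at least 69 patients. The 69 is a feasibility number with no event rate or precision behind it, so there is no planned figure to reproduce. The following are assumptions, because the documents do not give them:
- *m*, true 6-month mortality: 3%, 6% or 10%.
- *f*, share of source patients recruitable only at the clinic: 20% or 50%.
- *s*, share of those patients' deaths that fall before the clinic visit: 25%, 50% or 75%. Only deaths after DOAC start matter, since earlier deaths are outside the target population.

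**Mortality.** Per source patient, *mfs* deaths drop out of both numerator and denominator:

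observed = (m − mfs) / (1 − mfs) = m(1 − fs) / (1 − mfs)

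- m = 6%, fs = 0.2 × 0.25 = 0.05: 0.06 × 0.95 / 0.997 = 5.7%.
- m = 6%, fs = 0.5 × 0.75 = 0.375: 0.06 × 0.625 / 0.9775 = 3.8%.
- Smallest relative bias (m = 10%, fs = 0.05): 0.95 / 0.995 − 1 = −4.5%.
- Largest relative bias (m = 3%, fs = 0.375): 0.625 / 0.98875 − 1 = −36.8%.
- f = 0: no bias from this route.

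**mRS 0–1.** If only deaths are lost, the true proportion is divided by (1 − mfs). Over the same grid the inflation factor runs from 1/0.9985 = 1.002 to 1/0.9625 = 1.039, so the effect is favourable but small.

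**Primary composite.** Suppose only fatal events are lost and a share φ of events is fatal (also an assumption). With a true composite risk of 6%, observed = 0.06(1 − φfs) / (1 − 0.06φfs). Across fs = 0.05 to 0.375 the relative bias is:

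| φ | bias |
|---|---|
| 10% | −0.5% to −3.5% |
| 25% | −1.2% to −8.9% |
| 50% | −2.4% to −17.8% |

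**Does delayed entry repair it?** A simulation of 400,000 patients used a true 6-month risk of 10%, half entering uniformly over days 15–135 and the rest on day 10, with any event before entry barring entry.

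| Hazard | Naive risk | Delayed-entry Kaplan–Meier | True risk among those event-free at day 10 |
|---|---|---|---|
| Constant | 7.8% | 9.5% | 9.5% |
| Front-loaded | 5.9% | 7.7% | 7.7% |

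Delayed entry recovers the risk from the earliest entry time onwards. The gap from there to the full 10% is not recovered.

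**Scale against sampling error.** With 69 patients and m = 6%, expected deaths are 69 × 0.06 = 4.1. The two 6% examples give 69 × 0.0572 = 3.9 and 69 × 0.0384 = 2.6. The exact 95% interval for 4/69 is 1.6% to 14.2%.

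**The case against.** A reader might infer that nobody who dies or drops out early can be in the study. The protocol does not support that. Section 4.1 also allows enrolment during the first admission, and a patient enrolled there who later dies or is lost is in the cohort. The problem is confined to the clinic and referral route.

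A reader might also infer that the primary event rate as a whole is certainly too low. That is not established. Many composite events are non-fatal, and Section 5.2 collects in-hospital events and later bleeding or thrombotic events for everyone enrolled, so a survivor's earlier non-fatal event may still be recorded. Referral because of a complication could raise the rate. Early loss lowers it only if those lost had more events.

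Other points carry some weight. Consecutive sampling, the 3-month assessments and the baseline D-dimer all suggest that acute enrolment is the intended norm, so entry at month 5 would be an edge case. None of these bars late entry, however, and the consecutive-sampling sentence covers patients diagnosed on site, not referrals. Section 3 points to a study diagram that was not visible in the text reviewed; it may show the enrolment point and should be checked. The shift also lies well inside sampling error at this sample size, which limits its impact but does not remove a bias that works in one direction.

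Details of delayed entry could sit in an analysis plan that is not shown. The enrolment window, however, is protocol content, and the rules already fixed here (entry routes, clock from diagnosis, plain Kaplan–Meier) produce the bias if followed as written.

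**Conclusion.** The point holds for deaths. As written, patients reachable only through the clinic or by referral are selected for having survived to that visit, yet are counted as at risk from diagnosis. All-cause mortality and fatal primary events are biased low, and mRS 0–1 is biased favourably. For the full composite, downward is the likely direction but not a certain one.

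The size cannot be fixed from the documents. The range of about 5–37% applies to mortality only and rests entirely on the assumed 20–50% clinic-only share and 25–75% of those patients' deaths missed. It should not be carried over to the primary endpoint, where the effect depends on how many events are fatal and is smaller under the shares tried. If few patients enter late, the bias is close to nil.

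**What to change.** Record the dates of diagnosis, DOAC start and consent for every patient. In Section 6, state that each patient joins the risk set on the consent date (delayed entry), for the primary endpoint and for mortality alike. Events before consent are described separately and not counted in the 6-month rate. Report a sensitivity result restricted to patients enrolled in hospital; this is also the check for mRS 0–1, which delayed entry does not correct because it is not analysed as a time to event.

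Alternatively, add to Section 4.2 a maximum time from DOAC start to consent, chosen by the sponsor.

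Either change needs one or two sentences and no new procedure. The cost is a little less person-time, or a few late patients lost, and slightly wider intervals. Two limits remain. Delayed entry assumes that late entrants have the same risk from then on as patients already under follow-up. Neither change recovers the risk before the earliest entry time.

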### 4.2. Inclusion criteria

- Signed informed consent (ICF) to participate in the study
- Age  $\geq$  18 years
- Confirmed diagnosis of cerebral venous thrombosis (CVT) based on clinical presentation and neuroimaging, including one or more of the following:

MRI and MRV, AND/OR

CT and CTV, AND/OR

MRI or CT combined with DSA

- Initiation of DOACs within 5 to 15 days after starting treatment with heparin

### 4.3. Exclusion criteria

- CVT accompanied by antiphospholipid syndrome with all three positive laboratory criteria: lupus anticoagulant, anticardiolipin antibodies, and anti- $\beta$ 2-glycoprotein antibodies
- CVT in pregnant patients requiring continuous anticoagulation throughout pregnancy
- CVT with coexisting bleeding disorders, including immune thrombocytopenia with platelet count  $<100,000/\text{mL}$ , hemophilia A or B, von Willebrand disease, or a history of prolonged bleeding after surgery or invasive procedures
- CVT in patients with mechanical heart valves, atrial fibrillation, and moderate to severe mitral stenosis
- CVT in patients with a glomerular filtration rate (GFR)  $<15 \text{ mL/min}$
- CVT with severe hepatic impairment

